12.7 Reporting of Safety related events

Reporting to the Sponsor:

All SAEs, device deficiencies and health hazards that require measures are reported to the Sponsor by the PI (or authorized designee) within 24 hours after becoming aware of the event. Device deficiencies are assessed regarding their potential to lead to an SAE. DD are assessed regarding their potential to lead to an SAE.

12.7.1 Reporting to the Competent Ethics Committee:

The Sponsor reports to the CEC promptly any serious adverse event which has a causal relation with the MD, comparator or procedure/test method or where a causal relation appears to be possible.

In order to ensure prompt notification, the Sponsor may initially submit an incomplete notification.

If safety and health hazards that require measures must be taken immediately during the conduct of the investigation, the Sponsor notifies the CEC within 2 days of these measures and the circumstances which made them necessary.

12.7.2 Periodic safety reporting:

An Annual Safety Report (ASR) is submitted by the Sponsor to the CEC, yearly. The ASR contains a list of all SADEs and DDs and a report on their degree of seriousness, causal relationship with the MD and procedure and on subjects' safety.

12.8 Procedure

12.8.1 Initiation of Adverse Event Reporting

The Clinical Project Manager or designee will train the investigator and staff regarding the recording and reporting of adverse events. The sponsor shall implement and maintain a system to ensure that the reporting of the reportable events will be provided by the investigator to the sponsor immediately, but not later than 3 calendar days after investigation site study personnel's awareness of the event.

Adverse events (AEs) are recorded on the CRF by the sites. The following information should be recorded:

- The description of the event with enough detail to determine if the event meets the definition of a serious adverse event
- The date of the onset of the adverse event
- Relevant medical history leading up to the event
- A description of the action to treat the adverse event
- The site will also classify the event using the scales below

The investigator shall determine the AE Severity using the following scoring system which will be included on the CRF. The severity score is necessary is used to determine if the event meets the definition of a serious adverse event. The rating may also be used to determine if an adverse device event is unanticipated. This may be the case if the severity is greater than previously identified.

Rating	Description	Definition
5	Catastrophic	Patient Death
4	Critical	Permanent impairment or life threatening injury
3	Serious	Injury requiring medical intervention to prevent permanent impairment
2	Minor	Temporary injury that does not require medical intervention
1	Negligible	Inconvenience or temporary discomfort

The relationship between the use of the medical device (including the medical – surgical procedure) and the occurrence of each adverse event shall be assessed and categorized.

During causality assessment activity, clinical judgement shall be used and the relevant documents, such as the Investigator's Brochure, the Clinical Investigation Plan or the Risk Analysis Report shall be consulted, as all the foreseeable serious adverse events and the potential risks are listed and assessed there. The presence of confounding factors, such as concomitant medication/treatment, the natural history of the underlying disease, other concurrent illness or risk factors shall also be considered.

The above considerations apply also to the serious adverse events occurring in the comparison group.

For the purpose of harmonizing reports, each SAE will be classified according to four different levels of causality:

- 1. Not related
- 2. Possible
- 3. Probable
- 4. Causal relationship

The sponsor and the investigators will use the following definitions to assess the relationship of the serious adverse event to the investigational device, the comparator or the investigation procedure.

- 1. Not related: Relationship to the device, comparator or procedures can be excluded when:
 - the event has no temporal relationship with the use of the investigational device, or the procedures related to application of the investigational device;
 - the serious adverse event does not follow a known response pattern to the medical device (if the response pattern is previously known) and is biologically implausible;
 - the discontinuation of medical device application or the reduction of the level of activation/exposure (when clinically feasible) and reintroduction of its use (or increase of the level of activation/exposure), do not impact on the serious adverse event;
 - the event involves a body-site or an organ that cannot be affected by the device or procedure;
 - the serious adverse event can be attributed to another cause (e.g. an underlying or concurrent illness/ clinical condition, an effect of another device, drug, treatment or other risk factors);
 - the event does not depend on a false result given by the investigational device used for diagnosis, when applicable;
 - In order to establish the non-relatedness, not all the criteria listed above might be met at the same time, depending on the type of device/procedures and the serious adverse event.
- 2. Possible: The relationship with the use of the investigational device or comparator, or the relationship with procedures, is weak but cannot be ruled out completely. Alternative causes are

also possible (e.g. an underlying or concurrent illness/ clinical condition or/and an effect of another device, drug or treatment). Cases where relatedness cannot be assessed, or no information has been obtained should also be classified as possible.

- 3. Probable: The relationship with the use of the investigational device or comparator, or the relationship with procedures, seems relevant and/or the event cannot be reasonably explained by another cause.
- 4. Causal relationship: the serious adverse event is associated with the investigational device, comparator or with procedures beyond reasonable doubt when:
 - the event is a known side effect of the product category the device belongs to or of similar devices and procedures;
 - the event has a temporal relationship with investigational device use/application or procedures;
 - the event involves a body-site or organ that
 - the investigational device or procedures are applied to;
 - o the investigational device or procedures have an effect on;
 - the serious adverse event follows a known response pattern to the medical device (if the response pattern is previously known);
 - the discontinuation of medical device application (or reduction of the level of activation/exposure) and reintroduction of its use (or increase of the level of activation/exposure), impact on the serious adverse event (when clinically feasible);
 - other possible causes (e.g. an underlying or concurrent illness/ clinical condition or/and an effect of another device, drug or treatment) have been adequately ruled out;
 - harm to the subject is due to error in use;
 - the event depends on a false result given by the investigational device used for diagnosis, when applicable;

In order to establish the relatedness, not all the criteria listed above might be met at the same time, depending on the type of device/procedures and the serious adverse event.

The sponsor and the investigators will distinguish between the serious adverse events related to the investigational device and those related to the procedures (any procedure specific to the clinical investigation). An adverse event can be related both to procedures and the investigational device. Complications caused by concomitant treatments not imposed by the clinical investigation plan are considered not related. Similarly, several routine diagnostic or patient management procedures are applied to patients regardless of the clinical investigation plan. If routine procedures are not imposed by the clinical investigation plan, complications caused by them are also considered not related.

In some particular cases the event may not be adequately assessed because information is insufficient or contradictory and/or the data cannot be verified or supplemented. The sponsor and the Investigators will make the maximum effort to define and categorize the event and avoid these situations. Where an investigator assessment is not available and/or the sponsor remains uncertain about classifying the serious adverse event, the sponsor should not exclude the relatedness; the event should be classified as "possible" and the reporting not be delayed.

Particular attention shall be given to the causality evaluation of unanticipated serious adverse events. The occurrence of unanticipated events related could suggest that the clinical investigation places subjects at increased risk of harm than was to be expected beforehand. The site should determine and record if the AE was anticipated or unanticipated. If the risks for entering the study described in the informed consent / clinical brochure / clinical protocol or risk analysis reflect the nature, severity or degree of incidence of the AE, then it was anticipated. If not, then the AE is unanticipated.

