Adverse event possibly, probably or causally related to the use of an investigational device or procedures.

Serious Adverse Device Effect (SADE) (ISO14155)

Adverse device effect (ADE) that has resulted in any of the consequences characteristic of a serious adverse event.

Unanticipated Serious Adverse Device Effect (USADE) (ISO14155)

Serious adverse device effect (SADE) which by its nature, incidence, severity or outcome has not been identified in the current version of the risk analysis report.

Causal Relationship of SAE (MDCG 2020-10/1)

A causal relationship towards the medical device or the procedure of the investigation should be rated by the PI and the Sponsor as follows:

- Not related: The relationship to the device or procedures can be excluded.
- **Possible:** The relationship with the use of the investigational device is weak but cannot be ruled out completely. Alternative causes are also possible.
- **Probable:** The relationship with the use of the investigational device seems relevant and/or the event cannot reasonably be explained by another cause.
- **Causal relationship:** The serious event is associated with the investigational device or with procedures beyond reasonable doubt.

Investigational Medical Device:

A device that is assessed in a clinical investigation. Note: An investigational device can be a non-CE marked device or a CE marked device. The definition is understood to cover also the devices investigated in post-market surveillance investigations.

Case Report Form (CRF): A printed, optical, or electronic document designed to record all of the protocol required information to be reported to the sponsor on each trial subject.

Serious Health Threat:

signal from any adverse event or device deficiency that indicates an imminent risk of death or a serious deterioration in the health in subjects, users or other persons, and that requires prompt remedial action for other subjects, users or other persons

Note: This would include events that are of significant and unexpected nature such that they become alarming as a potential serious health hazard or possibility of multiple deaths occurring at short intervals.

Unanticipated / Unexpected Serious Adverse Device Effect (USADE)

- According to ISO 14155:2020: Serious adverse device effect which by its nature, incidence, severity or outcome has not been identified in the current risk assessment.

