12.3 Foreseeable adverse events and anticipated adverse device effects

There were no adverse device effects associated with the Hemanext RBC Processing System reported in the earlier in vivo pivotal human trial (cf. Investigator Brochure).

Well established blood transfusion complications (acute and delayed transfusion related effects) known to occur in medical practice using a conventional method of blood processing and storage will be considered as expected events. These effects are listed below³⁸:

- Transfusion-associated graft versus host disease
- Transfusion-related acute lung injury (TRALI)
- Post transfusion purpura
- Transfusion-associated circulatory overload (TACO)
- Transfusion-transmitted infection (TTI)
- Allergic reaction
- Transfusion-associated dyspnea (TAD)
- Febrile non-hemolytic transfusion reaction (FNHTR)
- Hypotensive transfusion reaction
- Delayed hemolytic transfusion reaction (DHTR)
- Delayed serologic transfusion reaction (DSTR)
- Acute hemolytic transfusion reaction (AHTR)
- Major cardiac event (MCE)
- Haematoma (bruise)
- Arterial puncture
- Delayed bleeding (re-bleeding)
- Nerve injury/irritation
- Localized infection/inflammation
- Deep venous thrombosis (DVT)
- Arteriovenous fistula
- Compartment syndrome
- Brachial artery pseudo-aneurysm

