12.8.3 Reporting Timelines

The sponsor must report to the CEC and as applicable, to all NCAs where the clinical investigation is authorized to start:

- For all reportable events as described in section 6.4 which indicate an imminent risk of death, serious injury, or serious illness and that requires prompt remedial action for other patients/subjects, users or other persons or a new finding to it: Immediately, but not later than 2 calendar days after awareness by sponsor of a new reportable event or of new information in relation with an already reported event.
 - This includes events that are of significant and unexpected nature such that they become alarming as a potential public health hazard. It also includes the possibility of multiple deaths occurring at short intervals. These concerns may be identified by either the NCA or the manufacturer.
- Any other reportable events as described in section 6.4 or a new finding/update to it: Immediately, but not later than 7 calendar days following the date of awareness by the sponsor of the new reportable event or of new information in relation with an already reported event.

12.9 List of foreseeable adverse events and anticipated adverse device effects, together with their likely incidence, mitigation or treatment

There are currently no adverse device effects associated with the Hemanext RBC Processing System reported in the earlier in vivo and pivotal human trial as reported in the Investigator Brochure. Hemanext RBC Processing System related potential Adverse Device Effects (including potential Serious Adverse Effects) may include, but are not limited to risks related to:

- Lack of sickle cell trait testing of RBC unit before processing and storage in the Hemanext RBC
 Processing System leading to high hemolysis and sickled red blood cells being transfused
 - A false negative on sickle trait testing of RBC unit before processing and storage in the Hemanext RBC Processing System leading to high hemolysis and sickled red blood cells being transfused
- Undetected leak in the HSB inner bag leading to a loss of sterility of the RBC unit. The product labeling is for fluid path sterility only.
- Use of a non-indicated additive solution with the Hemanext RBC Processing System leading to negatively affected quality of RBCs

The incidence is unknown. Mitigation of associated risk is achieved via continuous pharmacovigilance activities conducted during the study.

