13.2 Determination of Sample Size

10 burn patients and 10 patients with haematological malignancies, who require transfusion of red cell concentrate and who fulfil all eligibility criteria will be enrolled in this clinical investigation at Haukeland University Hospital.

A total of twenty patients will be sufficient to assess preliminary safety as the rate of transfusion related adverse events is usually low and if unexpected adverse events (any type or grade) should occur, this will be identified.

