6.1.9 Unanticipated Serious Adverse Device Effect

SADE which by its nature, incidence, severity, or outcome has not been identified in the current version of the risk analysis report.

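### The site rule for an anticipated event conflicts with the definition of an unanticipated serious device effect, so a more frequent, and possibly a more severe, known reaction may be labelled anticipated

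*Protocol*

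**What the plan says.** Several texts bear on whether an event counts as anticipated.

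- **Site rule, protocol section 12.8.1.** The site records each adverse event as anticipated or not. It is anticipated if the risks "described in the informed consent / clinical brochure / clinical protocol or risk analysis" are found to "reflect the nature, severity or degree of incidence of the AE, then it was anticipated". Otherwise it is unanticipated.
- **Severity sentence, also section 12.8.1.** The severity rating may be used to judge an adverse device event unanticipated: "This may be the case if the severity is greater than previously identified".
- **Definition, protocol section 12.1.** An unanticipated serious adverse device effect (USADE) is a serious adverse device effect "which by its nature, incidence, severity or outcome has not been identified in the current version of the risk analysis report". SAP section 6.1.9 repeats this: "SADE which by its nature, incidence, severity, or outcome has not been identified in the current version of the risk analysis report". SAP section 6.1.12 uses the same four attributes.
- **Expected list, protocol sections 12.3, 12.6 and 12.9.** Well-established complications "known to occur in medical practice using a conventional method of blood processing and storage will be considered as expected events". No limit on severity or frequency is attached.
- **Incidence, protocol section 12.9.** The heading promises likely incidence. For the potential device effects the text says: "The incidence is unknown. Mitigation of associated risk is achieved via continuous pharmacovigilance activities conducted during the study". The transfusion complications are listed without rates.
- **Use of the label.** Section 13.2 supports twenty patients partly on the ground that "if unexpected adverse events (any type or grade) should occur, this will be identified". SAP section 7.8.2 breaks serious adverse device effects down by anticipation. The sentence that follows, run into the 7.8.3 heading, leaves the classification of device effects to the clean file meeting and gives no criterion.

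**The concern.** For a modified red-cell product, one plausible safety signal is a familiar transfusion reaction that occurs more often, or more severely, than with conventional units. A classification rule should let such an event stand out. Read literally, the site rule does not: a reaction whose name appears in the consent form, brochure, protocol or risk analysis matches on nature, and that match is enough. The expected list reinforces this, because it settles the question by name. The USADE definition asks whether anything about the event is new, which is the opposite test.

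Three things use the label: the sample-size argument in section 13.2, the SAP breakdown by anticipation, and the remark in section 12.8.1 that related unanticipated events could point to increased risk. If the site and the SAP apply different rules, the same event can carry two labels, and the anticipation table depends on which one is carried forward.

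**Working it through.** The plan gives no figure to reproduce; SAP section 5.1 says there are no statistical criteria behind twenty patients. The check is a comparison of rules.

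**Step 1. Where the rules differ.** The site rule covers all adverse events, uses three attributes and accepts four reference documents. The USADE definition covers serious adverse device effects, uses four attributes (it adds outcome) and, in section 12.1 and SAP 6.1.9, refers to the risk analysis report alone. They can be compared where they overlap, on serious device effects.

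**Step 2. Count the disagreements.** Mark each attribute as covered or not covered, and suppose for the count that both rules look at the same reference.

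- Nature, severity and incidence: 2^3 = 8 patterns. The literal site rule says anticipated in 8 − 1 = 7 (all but none covered). The definition says unanticipated in 8 − 1 = 7 (all but all covered). They conflict in 8 − 2 = 6.
- With outcome: 2^4 = 16 patterns. The site rule says anticipated in 7 × 2 = 14. The definition says unanticipated in 16 − 1 = 15. They conflict in 14 − 1 = 13.

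Both texts turn on the word *or*, so other readings were counted too.

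| Site rule: anticipated if | Definition: unanticipated if | Opposite labels, 3 attributes | Opposite labels, 4 attributes |
|---|---|---|---|
| any one covered | any one not identified | 6 of 8 | 13 of 16 |
| all three covered | any one not identified | 0 of 8 | 1 of 16 |
| any one covered | none identified | 0 of 8 | 1 of 16 |
| all three covered | none identified | 6 of 8 | 13 of 16 |

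The first row takes each text at its most natural meaning. The severity sentence supports that reading of the definition, since it lets severity alone make an event unanticipated. No reading removes every conflict once outcome is included. If the site rule required all four attributes, the first-row conflict would fall to 0 of 16. These are counts of patterns, not probabilities.

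**Step 3. One event through the texts.** Take a severe acute hemolytic transfusion reaction rated possibly related. Section 12.3 makes it expected by name. The literal site rule makes it anticipated by nature. The severity sentence says it may be unanticipated. Section 12.1 makes it unanticipated if its severity, incidence or outcome is not in the risk analysis report, which is not among the documents reviewed. If the reaction is instead of ordinary severity but occurs too often, no sentence parallel to the severity one sends the site back to the question.

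**Step 4. What one case can show.** The documents give no background rates, so those here are assumptions. Twenty patients at two units give 40 hypoxic units, a floor because section 10.1 says at least two. The chance of at least one event of a single named type is 1 − (1 − r)^40: 33% at r = 1 in 100 per unit, 3.9% at 1 in 1,000 and 0.4% at 1 in 10,000. The lists in 12.6 and 12.9 have 23 entries. At an illustrative 1 in 1,000 for each, treated as independent, the chance of at least one listed event is 1 − 0.999^(40 × 23) = 1 − 0.999^920 = 60%. A single listed event is therefore not evidence of an excess.

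**The case against.** The strongest reply is that little turns on the site's label, and most of that stands. The primary outcome counts every adverse event of any type or grade. Reporting under section 12.8.2 depends on seriousness and causality, and only events rated not related are left out. The Data Monitoring Committee adjudicates all adverse events (section 3.6), and all are listed and tabulated by term, severity and causality (SAP section 7.8.1). The severity sentence gives a route for a worse reaction, though only a permissive one. The clean file meeting makes the final call on device effects, and the SAP's own definition is the stricter one.

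Four stronger conclusions might be inferred, and the documents do not support them.

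- **That a worse or more frequent known reaction would never be flagged.** The severity sentence, the reporting rule and the committee's review all contradict this.
- **That the USADE count would read zero despite a real excess.** This assumes the clean file meeting would ignore the definition in SAP sections 6.1.9 and 6.1.12.
- **That incidence cannot be judged at all.** Section 12.9 has no rates for the listed complications, but the risk analysis report and the brochure were not available and may contain some.
- **That one case of a rare reaction already exceeds background.** Step 4 shows why it does not.

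What the reply leaves unanswered is the inconsistency itself. The severity sentence has no counterpart for frequency, the clean file meeting has no stated criterion, and section 12.8.1 and the SAP name different decision-makers.

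**Conclusion.** The point holds as an inconsistency between rules. Taken literally, the site rule and the USADE definition give opposite labels in 6 of 8 patterns on the three shared attributes and 13 of 16 with outcome. They also differ in reference document and in who decides. A more frequent known reaction may be recorded by the site as anticipated. A more severe one may be too, but that limb is weaker because of the severity sentence.

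The consequence is confined to the anticipated/unanticipated label and to what rests on it: the SAP breakdown and the sample-size argument that unexpected events will be identified. The primary outcome, the reporting of related serious events and the committee's review are unaffected. The conclusion rests on reading *or* in section 12.8.1 as meaning that one match suffices. If all three attributes were meant, the conflict shrinks to 1 of 16, but the missing outcome attribute and the different reference documents remain.

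**What to change.** Use one rule throughout.

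1. In protocol section 12.8.1, state that an adverse event is anticipated only if its nature, severity, incidence and outcome are all covered by the current risk analysis report.
2. In sections 12.3, 12.6 and 12.9, state that the list settles nature only.
3. Bring the severity sentence in section 12.8.1 into line, so that severity beyond what the report identifies makes the event unanticipated.
4. In SAP section 7.8.2, state that the clean file meeting applies the rule of protocol section 12.1 and SAP section 6.1.9 when it fills the anticipation table.

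Do not add a default that labels every serious, possibly related listed reaction as unanticipated; that would leave the anticipation table uninformative. The sponsor should check that the risk analysis report gives frequencies for the listed reactions, because the incidence test needs them.

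The cost is wording in four protocol sections and one SAP line. The downside is that a few more events may be labelled unanticipated.
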